7.2. MULTICENTER STUDIES

This study will be conducted by multiple investigators at multiple centers in North America and Western Europe. Randomization to dosing groups will occur in a double-blind manner using an integrated IWRS, and will be stratified by the presence or absence of a history of or current esophageal stricture at Screening and history of a prior positive steroid response to any corticosteroid treatment previously received to treat the subject's EoE captured with demography.

Randomization to dosing groups is not stratified by country/center.

When specified, statistical analysis will be adjusted for geographic region or geographical region will be used as a subgroup. Geographic region will be categorized as follows:

Geographic Region	Country
North America	United States, Canada
Western Europe	Belgium, Germany, Switzerland and Spain

Document: Author: Version Number:

Version Date:

3.0

06NOV2019

Template No.: CS_TP_BS016 Revision 5 Reference: CS_WI_BS005

7.3. MISSING DATA

Missing efficacy data for the primary efficacy analysis will be imputed as described in sections 16.1.2 and 16.1.4 of this SAP.

Missing components of certain efficacy variables will be imputed prior to analysis/summarizing. This is described in the relevant secondary and exploratory endpoint analysis sections.

7.4. MULTIPLE COMPARISONS/ MULTIPLICITY

The primary analysis of the primary efficacy variable will be performed using a gatekeeping strategy to preserve Type I error. This strategy is described in section 16.1.3.

The analysis of the secondary efficacy parameter of number of dysphagia episodes will use a Holm-Step down procedure (Holm, 1979). This is described in section 16.2.3.4.

All other statistical testing performed is considered descriptive only and no adjustments will be performed for multiplicity.

7.5. EXAMINATION OF SUBGROUPS

Subgroup analyses will be conducted as stated in section 16.1.5. It should be noted that the study was not designed to detect treatment differences with high statistical power within subgroups.

The following subgroups will be assessed:

- History of or current presence of esophageal stricture:
 - o Yes
 - o No
- Prior positive steroid response to any corticosteroid treatment previously received to treat EoE:
 - Yes

Author:

Version Number: 3.0

Version Date: 06NOV2019

Template No.: CS_TP_BS016 Revision 5 Reference: CS_WI_BS005

Effective Date: 01Apr2018

Page 23 of 70

- No
- Geographic region:
 - o North America
 - Western Europe
- Gender:
- Female
- o Male
- Age (years):
 - \circ 18 < 30 years
 - \circ 30 < 45 years
 - \circ 45 < 65 years
 - \circ > = 65 years
- Race in 3 categories:
 - o Black/African American or Afro-Carribbean
 - o White
 - All other races combined (American Indian/Alaska Native, Asian, Native Hawaiian/Other Pacific Islanders)
- Ethnicity:
 - o Hispanic or Latino
 - Not Hispanic or Latino
- Proton Pump Inhibitor (PPI) status:
 - Continuing into the study
 - Not continuing into the study

8. OUTPUT PRESENTATIONS

Appendix 1 shows conventions for presentation of data in outputs.

Document:

Author: Version Number: 3.0

Version Date: 06NOV2019

Template No.: CS_TP_BS016 Revision 5 Reference: CS_WI_BS005

Effective Date: 01Apr2018

Page 24 of 70

The templates provided with this SAP describe the presentations for this study and the format and content of the summary tables, figures, and listings to be provided by IQVIA Biostatistics.

9. DISPOSITION AND WITHDRAWALS

All subjects who provided informed consent will be accounted for in this study.

Subject disposition and study discontinuations, including reasons for study discontinuation will be presented for the ENR set for the placebo run-in period prior to randomization.

Subject disposition and study discontinuations, including reasons for study discontinuation during Parts 1 and Part 2 will be presented for the ITT and FAS analysis sets. The number of histologic non-responders at Week 12 who received single-blind (to subject) APT-1011 3.0 mg BID in Part 2 will be presented.

For Part 2, disposition information will also be presented separately for histologic non-responders at Week 12 who received to single-blind (to subject) APT-1011 3.0 mg BID in Part 2.

Analysis set disposition and reasons for exclusion from the PP analysis set will be presented for all subjects in the ENR set.

Protocol deviations will be listed.

10. DEMOGRAPHIC AND OTHER BASELINE CHARACTERISTICS

Demographic data and other baseline characteristics will be presented for each of ENR set, the ITT analysis set, the FAS analysis set, and the SAF.

No statistical testing will be carried out for demographic or other baseline characteristics.

The following demographic and other baseline characteristics will be reported for this study:

- Sex (Male/Female)
- Race (White, Black or African American, Asian, American Indian or Alaska Native, Native Hawaiian or other Pacific Islander, Other)
- Ethnicity (Hispanic or Latino/Not Hispanic or Latino)
- Age (years) calculated relative to date of informed consent
- Geographic region (North America/Western Europe)
- Weight (kg)

Author:

Version Number: 3.0

Version Date: 06NOV2019

Template No.: CS_TP_BS016 Revision 5 Reference: CS_WI_BS005

Effective Date: 01Apr2018

Page 25 of 70

- Height (cm)
- Body mass index (BMI) (kg/m²)
- Smoking status (Never/Former/Current)
- Global EoE symptom score
- History of esophageal stricture(s) (Yes/No)
- Current esophageal stricture(s) based on the study esophagogastroduodenoscopy (EGD) (Yes/No)
- History of a positive steroid response to EoE treatment (Yes/No)
- PPI status (Continuing Yes/No)

10.1. DERIVATIONS

• BMI (kg/m^2) = weight (kg)/ height $(m)^2$

11. SURGICAL AND MEDICAL HISTORY

Surgical and medical history information will be coded using the Medical Dictionary for Regulatory Activities (MedDRA) coding dictionary, Version 21.0 and presented for the SAF.

- Surgical procedures captured on the *Medical and Surgical History* page of the eCRF will be presented by SOC (System Organ Class) and PT (Preferred Term).
- Medical history conditions are defined as those conditions which stop prior to or at Screening. Medical history
 conditions captured on the *Medical and Surgical History* page of the eCRF will be presented by SOC and PT.

12. CONCOMITANT ILLNESSES

Concomitant Illnesses will be coded using the MedDRA coding dictionary, Version 22.0 and presented for the SAF.

- Concomitant Illnesses are medical conditions (other than EoE) which started prior to or at Screening and are
 ongoing at the date of Screening. Concomitant illnesses captured on the *Medical and Surgical History* page of
 the eCRF will be presented by SOC and PT.
- Concomitant illnesses will be included in the medical history summary, and indicated as concomitant in the listings.

Document:

Author:

Version Number: 3.0

Version Date: 06NOV2019

Template No.: CS_TP_BS016 Revision 5 Reference: CS_WI_BS005

13. MEDICATIONS

Medications will be coded using the WHO Drug Dictionary (WHODD), 01 September 2017 and presented by ATC Level 3 and Preferred Term for the SAF. A modified Preferred Term has been provided by Adare and will be presented in the summary tables.

See Appendix 2 for handling of partial dates for medications, in the case where it is not possible to define a medication as prior, concomitant, or post treatment, the medication will be classified by the worst case; i.e. concomitant.

- 'Prior' medications are medications which started and stopped prior to the first dose of study drug.
- 'Concomitant' medications are medications which:
 - o started prior to, on or after the first dose of study drug
 - o AND ended on or after the date of first dose of study drug or were ongoing at the end of the study.
- 'Post' medications are medications which started after the last dose of study drug.

14. STUDY DRUG EXPOSURE

Exposure to study drug in weeks will be presented for the SAF. It will be derived separately for each of Part 1, Part 2 and for Parts 1 and Parts 2 combined.

- For Part 1 all subjects will be included in their double-blind dosing groups.
- For Part 2, histologic responders at Week 12 who continue into Part 2 will be included in their double-blind dosing groups.
- For Part 2, histologic non-responders at Week 12 who continue into Part 2 will be included in a single-blind APT-1011 3.0 mg BID group. Additionally, a summary will be provided for all APT-1011 3.0 mg BID during Part 2, both double-blind and single-blind.
- For Parts 1 and 2 combined, histologic non-responders at Week 12 will be included in their double-blind dosing group (counting just their Part 1 exposure) and also in the single-blind APT-1011 3.0 mg BID group (counting just their Part 2 exposure). A summary will be provided for all APT-1011 3.0 mg BID during Part 2, both double-blind and single-blind.

The date of first study drug administration in Part 1 will be taken from the eCRF "Sparse Pharmacokinetic Sampling" form. The date of last study drug will be estimated using study visits. For subjects who complete the

Author:

Version Number: 3.0

Version Date: 06NOV2019

Template No.: CS_TP_BS016 Revision 5 Reference: CS_WI_BS005

Page 27 of 70

Week 12 visit, the last dose of study drug for part 1 will be assumed to be on the morning of the date of that visit. For subjects who complete the Week 52 visit, the last dose of study drug for part 2 will be assumed to be the evening before this visit. For subjects who discontinue the trial prior to either of these dates, date of last dose will assumed to be their early termination visit.

Compliance will be assumed to be 100%, interruptions and dose changes are not taken into account for duration of exposure.

Study drug exposure time will be divided into 5 categories, such that an equal number of subjects falls into each catgory (i.e. 20th, 40th, 60th, and 80th percentiles of exposure time will be used as cut-offs).

14.1. DERIVATIONS

Duration of exposure (weeks) for Part 1=

(date of last study drug administration in Part 1 – date of first study drug administration in Part 1 + 1 / 7.

Duration of exposure (weeks) for Part 2=

(date of last study drug administration in Part 2 – date of first study drug administration in Part 2 + 1 / 7.

Duration of exposure (weeks) for Parts 1 and 2 combined, for histological responders at Week 12 =

(date of last study drug administration in the study – date of first study drug administration in Part 1+1) / 7.

Total exposure to study drug for Part 1 =

(Duration of exposure (days) * total daily dose) – evening dose.

Duration of exposure for Part 2 =

(Duration of exposure (days) * total daily dose)

15. STUDY DRUG COMPLIANCE

Compliance to study drug will be summarized for the ITT and FAS analysis sets.

Detailed study drug accountability data will not be available to IQVIA Biostatistics.

Compliance is to be assessed by the investigator and their assessment of compliance at each visit reported as either

Document:

Author: Version Number: 3.0

Version Date: 06NOV2019

Template No.: CS_TP_BS016 Revision 5 Reference: CS_WI_BS005

Effective Date: 01Apr2018

Page 28 of 70

compliant or non-compliant. The protocol defines non-compliance as 'taking less than 80% or more than 120% of study drug during any evaluation period (visit to visit)'.

Summaries of proportions of compliant/non-compliant subjects at each study visit will be provided. These summaries will not include data for histologic non-responders at Week 12 after they receive single-blind (to subject) APT-1011 3.0 mg BID at the start of Part 2. i.e. only information while subjects are taking their randomized study drug will be included.

Document:

Author: Version Number: 3.0

Version Date: 06NOV2019

Template No.: CS_TP_BS016 Revision 5 Reference: CS_WI_BS005

16. EFFICACY OUTCOMES

16.1. PRIMARY EFFICACY

16.1.1. PRIMARY EFFICACY VARIABLE & DERIVATION

The primary efficacy variable is the following histological endpoint:

Percentage of subjects with ≤6 peak eosinophils/HPF after assessing at least 5-6 biopsies from the proximal and distal esophagus (~3 each) where the HPF area is 235 square microns (40 magnification lens with a 22 mm ocular).

The assessment or response is performed by the pathologist and will not be derived by IQVIA Biostatistics.

16.1.2. MISSING DATA METHODS FOR PRIMARY EFFICACY VARIABLE

For the primary analysis of the primary efficacy variable, any subject who does not meet the definition of responder, will be classified as a non-responder. This includes subjects who withdraw from the study prior to the week 12 histological assessment.

The primary analysis of the primary efficacy variable is via a stratified Cochran-Mantel-Haenzel (CMH) test, as described in section 16.1.3.

A sensitivity analysis, described in section 16.1.4 will be performed with missing response data imputed using multiple imputation, assuming the data are missing at random.

Multiple imputation will be used to provide estimates of the common odds ratio, its 90% confidence interval and associated 1-sided p-value.

The dataset containing subject, dosing group, week 12 histologic response, the two randomization strata, history of asthma/allergy, baseline EREF score, and PPI status will be used as the basis for multiple imputations. Histologic response will be set to missing for those subjects who did not have a Week 12 result for peak eosinophils/HPF (and for whom response status was set to non-responder in the primary efficacy analysis).

The methodology which follows in this section are taken from a 2013 paper by Ratitch, Lipkovich and O'Kelly. The imputation method will be based on logistic regression using the MONOTONE statement of PROC MI in SAS

Author:

Version Number: 3.0

Version Date: 06NOV2019

Template No.: CS_TP_BS016 Revision 5 Reference: CS_WI_BS005

Page 30 of 70

as shown below.

The option NIMPUTE in the PROC MI statement will be used to specify the number of imputed datasets to be generated. The output dataset will contain 500 copies of the original dataset, with the observed values being the same across all datasets, and with imputed values varying from one dataset to another. These multiple copies will be identified by a new variable, Imputation, added to the output dataset by PROC MI.

The SAS Code to perform the imputations is provided below. The SEED and NIMPUTE value are explicitly stated here to enable results to be replicated and quality assured.

```
PROC MI DATA=datain OUT=datain mi SEED=1201913 NIMPUTE=500;
VAR dosegrp strata1 strata2 asthma EREF PPI response;
CLASS dosegrp strata1 strata2 response;
MONOTONE LOGISTIC;
RUN;
```

where dosegrp has 5 levels corresponding to the 5 dose groups (including placebo), strata1 and strata2 are the binary randomization strata, asthma is a binary variable for history of asthma/allergy (yes/no), and EREF is continuous variable for EREF score at baseline, PPI is a binary variable for PPI status (continuing into study vs not) and response is the binary response variable.

After imputation is performed, the next step will be analyzing each of the imputed datasets. This will be done using the same method (stratified CMH test) that was used for the primary efficacy analysis.

The SAS Code provided below is for one of the pairwise tests, assuming that dosegrp = 1 represents the APT-1011 3.0 mg BID group and dosegrp = 5 represents the placebo group. All of the analyses of imputed datasets described below and the combining of relevant statistics to provide overall imputed estimates of odds ratio, 90% confidence interval and 1-sided p-values would need to be performed separately for each of the four APT-1011 dosing groups and placebo.

```
*** Obtain Mantel-Haenzel estimate of the common odds ratio for APT-1011 3mg
BID vs Placebo adjusted for
randomization strata ***;
PROC FREQ DATA=datain mi(where=(dose in (1,5)));
TABLES stratal*strata2*dosegrp*response/CMH;
ODS OUTPUT COMMONRELRISKS=comrrout;
BY Imputation_;
RUN;
```

The estimates of odds ratios follow a log-normal distribution and a log transformation will be applied to normalize

 Document:
 Version Number: 3.0

 Author:
 Version Date: 06NOV2019

 Template No.: CS_TP_BS016 Revision 5
 Reference: CS_WI_BS005

Template No.: 00_11 _Booto Neviolon o

Page 31 of 70

these estimates in order to be able to apply Rubin's (Rubin, 1987) combination rules. These combination rules take as input estimates of a statistic obtained from multiple imputed datasets as well as standard errors of these estimates, and produce an overall pooled estimate and an overall standard error and confidence interval.

The SAS code provided below shows a log transformation applied to the estimates of the odds ratio for the treatment effect. Standard error of the transformed estimate is obtained from the log-transformed lower and upper confidence limits for the odds ratio estimate. Then the dataset containing the transformed estimates and their standard errors is passed to PROC MIANALYZE. The MODELEFFECTS statement contains a name of the variable that represents an estimate of the statistic to be combined, and the STDERR statement contains the name of the variable that represents standard errors of that estimate. The combined results are captured in the dataset

PARAMETERESTIMATES. The combined estimate of the odds ratio can then be back-transformed to its original log scale as shown in the last data step of SAS Code, which also computes 90% confidence limits on the log scale using the combined estimate of the standard error for the odds ratio.

```
*** Log-transform odds ratio estimates
and obtain standard error from confidence intervals ***;
DATA ormh t;
SET comrrout(WHERE=(StudyType="Case-Control"));
log or mh value=log(VALUE);
log or mh se=(log(UPPERCL) - log(LOWERCL)) / (2*1.96);
RUN:
*** Combine transformed estimates;
PROC MIANALYZE DATA=ormh t;
ODS OUTPUT PARAMETERESTIMATES=mian ormh t;
MODELEFFECTS log or mh value;
STDERR log or mh se;
RUN;
*** Back-transform combined values;
DATA mian mhodds bt;
SET mian lgsodds t;
Estimate back = EXP(ESTIMATE); *Pooled odds ratio;
LCL back=Estimate back*EXP(-1.645*STDERR); *Pooled lower limit;
UCL back=Estimate back*EXP(+1.645*STDERR); *Pooled upper limit;
RUN:
```

The CMH general association statistic test, under the null hypothesis of no association between APT-1011 dose and placebo, having controlled for the randomization strata has an asymptotic chi-square distribution with 1 degree of freedom. The chi-square distribution with 1 degree of freedom is highly skewed and obtaining a combined result of the CMH test from multiply-imputed data requires a transformation that would normalize the CMH statistic.

Author:

Version Number: 3.0

Version Date: 06NOV2019

Template No.: CS_TP_BS016 Revision 5 Reference: CS_WI_BS005

The Wilson-Hilferty transformation (Wilson & Hilferty, 1931; Goria, 1992) can be used for this purpose:

$$wh_cmh^{(m)} = \sqrt[3]{cmh^{(m)}/df} \quad (1)$$

where $cmh^{(m)}$ is the CMH statistic computed from the mth imputed dataset, df is the number of degrees of freedom associated with the CMH statistic, and $wh_cmh^{(m)}$ is the transformed value. The transformed statistic is approximately normally distributed with mean $1 - 2/(9 \times df)$ and variance $2/(9 \times df)$ under the null hypothesis.

The transformed statistic in (1) can be standardized to obtain a variable that is normally distributed with mean 0 and variance 1:

$$St_{wh_cmh}^{(m)} = \frac{\sqrt[3]{cmh^{(m)}/df} - \left(1 - \frac{2}{9 \times df}\right)}{\sqrt[2]{\frac{2}{9 \times df}}}$$
(2)

This transformed statistic can be passed to PROC MIANALYZE in SAS in order to perform a combined CMH test. The SAS code below contains an invocation of PROC FREQ to request the CMH test using the CMH option in the TABLES statement, with the results captured in the ODS output dataset CMH. A subsequent data step applies the Wilson-Hilferty transformation as described in equation (2) and then passes the transformed values to PROC MIANALYZE using the same syntax as for the odds ratio.

Finally, a p-value (probt_upper) for the combined CMH test can be obtained as the upper-tailed p-value from the normal test produced by PROC MIANALYZE on the transformed statistic. This is done in the last data step of the SAS Code below.

```
*** Perform CMH test;
PROC FREQ DATA=datain_mi(where=(dose in (1,5)));
TABLES strata1*strata2*dosegrp*response/CMH;
ODS OUTPUT CMH=cmh;
BY _Imputation_;
RUN;

*** Apply Wilson-Hilferty transformation to the CMH statistic and standardize the resulting normal variable;
DATA cmh wh;
SET cmh(WHERE=(AltHypothesis="General Association"));
```

Document:

Author: Version Number: 3.0

Version Date: 06NOV2019

Template No.: CS_TP_BS016 Revision 5 Reference: CS_WI_BS005

Effective Date: 01Apr2018

Page 33 of 70

```
cmh value wh=((VALUE/DF)**(1/3) - (1-2/(9*DF)))/SQRT(2/(9*DF));
cmh_sterr_wh = 1.0;
RUN;

*** Combine results;

PROC MIANALYZE DATA=cmh wh;
ODS OUTPUT PARAMETERESTIMATES=mian_cmh_wh;
MODELEFFECTS cmh_value_wh;
STDERR cmh_sterr_wh;
RUN;

*** Compute one-sided p-value;
DATA mian cmh wh_p;
SET mian cmh wh;
IF tValue > 0 THEN Probt_upper = Probt/2;
ELSE Probt_upper = 1-Probt/2;
RUN;
```

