#### **Treatment Failure**

Subjects who develop food impaction with or without esophageal dilatation ANYTIME during the study will be considered treatment failures and complete early termination assessments and exit the study after the 2-week post-treatment follow-up period. Subjects who voluntarily withdraw from the study due to worsening symptoms before the Week 12 evaluation or later in the study will also be considered treatment failures. Every effort should be made to perform an EGD in subjects wishing to withdraw due to worsening symptoms. They also must complete the early termination assessments and exit the study after a 2-week post-treatment follow-up period.

A brief overview of how responder status will be determined is discussed in Section 4.1.6; this will be fully described in the investigator site file (ISF).

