#### 8.0 STATISTICS

## 8.1 Determination of Sample Size

Part 1 includes a sample size with 100 subjects, in which 20 patients are randomized each to 1.5 mg HS, 1.5 mg BID, 3 mg HS, 3 mg BID, and placebo in the ratio 1:1:1:1:1. See also the discussion of randomization in Section 4.1.5.2.

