## 8.1.1 Expected Number of Subjects by Part

The following assumptions were used:

- The 1:1:1:1 (1.5 mg HS: 1.5 mg BID: 3 mg HS, 3 mg BID: placebo) randomization ratios will remain constant throughout the study.
- Based on these randomization ratios, approximately 80% of all subjects in Part 1 will be treated with an APT-1011 dosing regimen and approximately 20% of all subjects in Part 1 will be treated with placebo.
- Based upon the PR-021 study, which had slightly different histologic response criteria, it is expected that approximately 60% of patients on active treatment are expected to be a histologic responder compared to 10% on placebo. The lowest dose may be less effective.
  - Assuming a 60% histologic response rate for the 3 highest active doses of 1.5 mg BID, 3 mg HS, 3 mg BID, a 20% response rate for 1.5 mg HS, and a 10% response rate for placebo, it is expected that overall approximately 50% of active treatment will be responders at Week 12 (40 out of 80).
  - o It is expected that at Week 26 an additional 20% will drop out who were previously responders and of the PART 1 non-responders that 40% will still be non-responders.
  - After Week 26, of the remaining subjects, it is expected that approximately 20% will dropout before Week 52.

Given these assumptions, it is expected that approximately 42 patients will be responders and complete Week 26, and about 34 of those responders will complete Week 52.

The power for testing each active dose versus placebo given a histologic response rate of 60% active treatment and 10% placebo for the primary endpoint (Part 1) is equal to 97.5% (one-sided Type I error = 0.05). Additionally, the power for achieving statistical significance for all 3 of the highest active doses of 1.5 mg BID, 3 mg HS, 3 mg BID via the gatekeeping hypothesis testing approach assuming independence is approximately 0.93.

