## 8.8 Efficacy Analyses

#### 8.8.1 Efficacy Analysis for Part 1

The primary efficacy endpoints for Part 1 is detailed in Section 6.2.8.

Let  $\theta_j$  be the Cochran-Mantel-Haenzel common odds ratio comparing treatment vs. control for histologic response for dose j given randomization strata; with j=1,2,3,4 corresponding to APT-1011 3 mg BID, 1.5 mg BID, 3 mg HS, 1.5 mg HS doses, respectively. There are 4 hypotheses corresponding to the 4 active doses, which will be tested using a gatekeeping strategy to preserve Type I error for each analysis.

1) Primary Hypothesis #1

 $H_0: \theta_1 \leq 1$ 

 $H_1: \theta_1 \leq 1$ 

A stratified Cochran-Mantel-Haenzel test will be used to test primary hypothesis #1, i.e., 3 mg BID vs. placebo, using the randomization strata. If the corresponding one-sided p-value is less than or equal to 0.05, the null hypothesis will be rejected, and subsequently the following hypothesis will be tested:

2) Primary Hypothesis #2

 $H_0: \theta_2 \leq 1$ 

 $H_1: \theta_2 \leq 1$ 

A stratified Cochran-Mantel-Haenzel test will be used to test primary hypothesis #2, i.e., 3 mg HS vs. placebo. If the corresponding one-sided p-value is less than or equal to 0.05, the null hypothesis will be rejected, and subsequently the following hypothesis will be tested:

3) Primary Hypothesis #3

 $H_0: \theta_3 \leq 1$ 

 $H_1: \theta_3 \leq 1$ 

A stratified Cochran-Mantel-Haenzel test will be used to test primary hypothesis #3, i.e., 1.5 mg BID vs. placebo. If the corresponding one-sided p-value is less than or equal to 0.05, the null hypothesis will be rejected, and subsequently the following hypothesis will be tested:

4) Primary Hypothesis #4

 $H_0: \theta_4 \leq 1$ 

H₁: θ₄≤1

A stratified Cochran-Mantel-Haenzel test will be used to test primary hypothesis #4, i.e., 1.5 mg HS vs. placebo. If the corresponding one-sided p-value is less than or equal to 0.05, the null hypothesis will be rejected.

Note the gatekeeping strategy only allows formal hypothesis testing of 1.5 mg HS or 1.5 mg BID if the higher doses meet statistical significance. Given prior studies with histologic endpoints, there is a strong rationale suggesting that higher doses will have a greater benefit on the primary efficacy endpoint of histology.

#### 8.8.2 Efficacy Analysis for Part 2

Sustained EoE response will be assessed in subjects who complete both Part 1 and Part 2 and complete Week 26 evaluations. This will be assessed by the primary endpoint.

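### The missing-at-random imputation gives early treatment failures without a Week 12 biopsy the response rate of completers in their arm, although the primary analysis counts them as non-responders

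*SAP*

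**What the plan says.** Protocol 4.1.1 makes food impaction at any point in the study a treatment failure that leads to exit. It adds that subjects who withdraw because their symptoms get worse, before Week 12 or later, "will also be considered treatment failures". Histologic responder, histologic non-responder and treatment failure are three separate definitions there.

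SAP 16.1.2 has two rules for the Week 12 response. In the primary analysis, anyone who does not meet the responder definition is a non-responder, including those who withdraw before the Week 12 histology. For the multiple-imputation analysis, "Histologic response will be set to missing for those subjects who did not have a Week 12 result" for peak eosinophils. The imputation model holds dose group, the two randomization strata, asthma/allergy history, baseline EREFs score and PPI status. It contains no treatment-failure flag, discontinuation reason or post-baseline symptom measure.

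SAP 6.3 does not re-map end-of-treatment visits and SAP 6.5 applies no windows. A biopsy taken at early termination therefore does not become a Week 12 result.

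SAP 16.1.4 lists three sensitivity analyses: the per-protocol set, covariate-adjusted logistic regression, and this imputation. Protocol 8.5 also promises tipping point analyses. The SAP contains none, and SAP 3.3 does not list the omission among its changes from the protocol.

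**The concern.** Missing at random here means that a subject who left with food impaction or worsening symptoms has the same chance of histologic response as a completer in the same arm with similar baseline values. Of all subjects without a Week 12 count, these are the ones for whom that is least plausible. Nothing in the model can tell them apart from someone who moved away.

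If failures are about equally frequent across arms, the imputation adds more responders where the completer rate is high than where it is low. The analysis meant to probe the primary result would then report a larger effect at the higher doses the more failures there are. With no tipping point analysis in the SAP, nothing in it would test the primary result against a less favourable assumption.

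**Working it through.** **Inputs from the documents**
- Arm size (protocol 8.1): "in which 20 patients are randomized each to 1.5 mg HS, 1.5 mg BID, 3 mg HS, 3 mg BID, and placebo".
- Response rates (protocol 8.1.1): "Assuming a 60% histologic response rate for the 3 highest active doses of 1.5 mg BID, 3 mg HS, 3 mg BID", and "a 20% response rate for 1.5 mg HS, and a 10% response rate for placebo".
- Stated power (protocol 8.1.1): "for the primary endpoint (Part 1) is equal to 97.5% (one-sided Type I error = 0.05".

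**Assumed, because the documents do not give it**
- The number of failures before Week 12 without a Week 12 count: *k* = 1 to 4 per arm of 20 (5% to 20%).
- All missing results belong to failures.
- The planning rates are taken over all 20 subjects, so responders number 12 at a higher dose, 4 at 1.5 mg HS and 2 on placebo.

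**Plan's own figure.** For 60% versus 10%, n = 20 per arm, one-sided 0.05, with pooled variance under the null:
- Null standard error: √(2 × 0.35 × 0.65 / 20) = 0.1508.
- Alternative standard error: √((0.60 × 0.40 + 0.10 × 0.90) / 20) = 0.1285.
- z = (0.50 − 1.645 × 0.1508) / 0.1285 = 1.96, so power is 0.975, as stated.
- Three doses jointly: 0.975³ = 0.927, matching the plan's figure, which it gives as "assuming independence is approximately 0.93".

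**Rate given to a failure.** It is about the completer rate of the arm. If the planning rates are completer rates, that is 60% at three doses, 20% at 1.5 mg HS and 10% on placebo. The average over the four active arms is (3 × 0.60 + 0.20) / 4 = 50%. If they are rates over all 20, the completer rate is 12/(20 − *k*), or 63% to 75%, at a higher dose; 4/(20 − *k*), or 21% to 25%, at 1.5 mg HS; and 2/(20 − *k*), or 11% to 12.5%, on placebo.

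**Effect on the odds ratio, equal failures per arm.** With failures held as non-responders, the odds ratio is (12 × 18)/(8 × 2) = 13.5 for a higher dose and (4 × 18)/(16 × 2) = 2.25 for 1.5 mg HS. Among completers it is [12/(8 − *k*)] / [2/(18 − *k*)] and [4/(16 − *k*)] / [2/(18 − *k*)] respectively. The imputed values come from a simplified version of the SAP method: arm-level logistic imputation, 2,000 draws, Rubin's rules and an unstratified odds ratio.

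| *k* per arm | Higher dose vs placebo, imputed rates | Difference, points | OR, completers | OR, imputed | 1.5 mg HS OR, completers | 1.5 mg HS OR, imputed |
|---|---|---|---|---|---|---|
| 1 | 63.1% vs 10.7% | 52.4 | 14.6 | 14.5 | 2.27 | 2.28 |
| 2 | 66.6% vs 11.3% | 55.3 | 16.0 | 16.1 | 2.29 | 2.28 |
| 3 | 70.5% vs 12.1% | 58.4 | 18.0 | 18.0 | 2.31 | 2.32 |
| 4 | 74.6% vs 12.9% | 61.7 | 21.0 | 20.9 | 2.33 | 2.30 |

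The difference with failures held as non-responders is 50 points. The one-sided p-value for a higher dose goes from 0.0015 to between 0.0013 and 0.0007.

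**Unequal failures, higher dose**
- 2 active, 4 placebo: (12/6)/(2/14) = 14.0; the imputed value is also 14.0.
- 4 active, 2 placebo: (12/4)/(2/16) = 24.0; the imputed value is also 24.0.
- 0 active, 4 placebo: (12/8)/(2/14) = 10.5, and the difference is 60% − 2/16 = 47.5 points. Imputation is then less favourable to active drug than the primary rule.

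**The case against.** The strongest defence is that the endpoint is purely histologic. Protocol 4.1.1 does not say that a treatment failure is a histologic non-responder, and protocol 2.1 links impaction to rings and strictures, which does not fix the eosinophil count. For a failure without a Week 12 biopsy the clinical outcome is known and the endpoint value is missing. Scoring it as non-response is a choice of estimand, which the primary analysis already makes. A missing-at-random analysis set beside non-responder imputation is a common contrast and shows how far the result depends on the non-responder rule.

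Most of that stands. A reader might infer that these subjects have a known bad Week 12 outcome that the imputation overwrites; the documents do not support this, because the histology was not observed at that visit. What remains is that completers of the same arm are a poor stand-in for these subjects. The model has nothing to correct for that, and any early-termination biopsy is left unused.

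Two other strong readings also fail. One is that failures on active drug are mostly imputed as responders. That holds at three doses, but at 1.5 mg HS about 75% to 80% would be imputed as non-responders, and the planned average over active arms is 50%. The other is that the imputation always favours active drug, whereas the unequal-failure cases show that the direction depends on where the failures fall.

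**Conclusion.** The point holds as a weakness of a sensitivity analysis. Failures before Week 12 without a Week 12 count are imputed at about their arm's completer rate, in conflict with how the primary analysis treats them. With 1 to 4 failures per arm, equal in both arms, the odds ratio for a higher dose moves from 13.5 to between 14.5 and 20.9. For 1.5 mg HS the shift is negligible on the same assumption (2.25 to at most 2.32). It nearly vanishes for a higher dose with 4 placebo and 2 active failures, and reverses if failures are mainly on placebo.

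These sizes rest on assumed failure counts, on every missing result being a failure, and on a simplified imputation without the baseline covariates or stratification. Failures who do have a Week 12 result keep their observed value.

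A reader might infer that the primary conclusion is at risk. It is not: the gatekeeping decision uses only the non-responder-imputed test, where "If the corresponding one-sided p-value is less than or equal to 0.05, the null hypothesis will be rejected", and the imputation does not enter it.

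**What to change.** In the imputation dataset, keep response = 0 for subjects who met the protocol 4.1.1 treatment-failure definition before Week 12 and have no Week 12 eosinophil result. Impute only results missing for other reasons. Report the number of such failures by arm, so that the reader can see whether the change matters.

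The cost is a small derivation. The discontinuation reasons in protocol 4.2.3 have no separate category for food impaction or worsening symptoms, so the flag has to be defined. It can be built from the discontinuation reason recorded at the Early Termination Visit and from the food-impaction and EGD records that SAP 16.2.1.11 already uses.

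Also run the tipping point analysis promised in protocol 8.5, or list its removal in SAP 3.3 with the reason. Protocol 2.5 already reports the Week 12 primary result, so any rerun must be labelled as added after the Week 12 unblinding.
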